6. STUDY POPULATION

6.1. Target Sample. The target sample for analyses is $N=600$ college student drinkers: 300 from Brown University, and 300 from the University of Houston. We will randomize 100 eligible students from each site to the CAA ($n=200$), PNF ($n=200$), and AO ($n=200$) conditions.

6.2. Inclusion Criteria. Inclusion criteria are:

(1) **Age 18-26.** The age range of 18-26 (a) coincides with the distinct developmental period of “emerging adulthood” (Arnett, 2005), (b) is characterized by a high prevalence of heavy episodic drinking (Johnson et al., 2012), and (c) is representative of college students, the majority of whom are 26 years of age or younger (Digest of Education Statistics: 2012).

(2) Male or female student at Brown University or University of Houston. The present study represents a first step in using counter-attitudinal advocacy activities in an attempt to reduce risky drinking behavior. As such, we focus on college students because they exhibit high rates of heavy episodic drinking (Johnson et al., 2012), and their identification with other college peers facilitates the testing of the enhanced manipulation. We recruit at 2 sites that differ in drinking patterns and demographics and geographic location to evaluate the generalizability of the study findings. The findings could have implications for alcohol abuse prevention both with college students and young adults more broadly.

(3) Past month heavy episodic drinking (for men, ≥ 5 drinks in one day, for women ≥ 4 drinks in one day). The 4/5 drink cutoff has been widely used as an indicator of risk ([name], Larimer, & Lewis, 2004; Wechsler & Nelson, 2001) and as a screening criterion in intervention studies targeting heavy drinking students. Our preliminary studies show that heavy drinking frequency is significantly correlated with attitudes towards moderate ($r = -.42$) and heavy ($r = .45$) drinking. By including only drinkers who have reported heavy episodic drinking we optimize the likelihood that developing arguments in favor of moderate drinking ($<4/5$ drinks/occasion) will constitute counter-attitudinal advocacy, and create dissonance between the espoused attitude in favor of moderation and recent behavior.

(4) At least two self-reported negative consequences from drinking in the past month. Because the CAA prompt involves writing arguments about avoiding alcohol-related problems, it will be necessary to ensure participants report at least two alcohol-related problems. Note that in 2 separate samples of college drinkers we found that 91% and 87% of those who met gender-specific binge criteria also reported at least 2 alcohol-related problems.

6.3. Exclusion Criteria. Exclusion criteria are: (1) **Status as a graduating senior.** Any student with senior status in the spring semester will be excluded from participating in the RCT, because of potential difficulties in contacting graduated students for follow-ups. Also, post-graduation drinking patterns may change substantially (White, Labouvie, & Papadaratsakis, 2005). (2) **Status as a third-year student at Brown (AY 2019-2020 only)** During the 2019-2020 academic year ONLY, third-year students will not be recruited at Brown University due to a conflict with another study.

7. ENROLLMENT

7.1 Recruitment and Enrollment Procedure Overview

We aim to recruit 600 heavy drinking students (300 each from UH & Brown), between 18-26 years of age, from the general student bodies of both institutions. Interested students who respond to recruitment solicitations will have the opportunity to complete a brief confidential web-based survey. Students will be eligible to participate in the RCT if they report (a) at least one gender-specific episode of heavy drinking in the previous month (4/5 or more drinks on a single occasion for women/men), (b) experiencing at least two alcohol-related problems in the previous month, and (c) status as an undergraduate who is not graduating within the 6-month study period. Due to conflicts with other studies at Brown University, during the 2019-2020 academic year we did not recruit third-year students or any student who has participated in a focus group/interview study on alcohol in the past 2 months. Students will be notified at the completion of the screening survey of their eligibility to participate. Screening and scheduling of baseline assessments (for those who meet screening criteria) will occur online at the same time. At each assessment point, participants will have the option to download a Resource Sheet with contact information for substance abuse and mental health services.

7.1.1 Brown recruitment

At Brown University, participants are recruited using several different methods. Primary recruitment methods include announcements posted on (a) campus-wide Today@Brown daily email listserv, (b) university group listservs serving clubs and student organizations (c) social

media platforms (e.g., Facebook, Instagram, etc.), (d) university-managed Facebook pages, (e) to the Center for Alcohol and Addiction Studies “Find a Study” page, (f) flyers posted near high traffic areas on campus (see representative materials in Appendix A, Recruitment Materials) and (g) snowball recruitment, in that participants will be invited to refer others they know to the study. Recruitment announcements include study-related information, eligibility requirements, and a link to a screener survey. Secondary recruitment methods include placing table slips in the dining halls with a study-specific number to text to receive a link to the screener and a QR code to scan. No in-person recruitment will occur at Brown. Under supervision and training of the PI, the senior Research Assistant and graduate Research Assistant will be responsible for the creation of online recruitment advertisements and dispersing/posting of flyers.

7.1.2 UH recruitment

At the University of Houston, we will invite a random sample of students from UH (without replacement) via email. Using email addresses provided by the Registrar, participants will be invited through the use of staggered email bursts. We will send the email bursts in cohorts of 1000- 4000 until the desired N is achieved. Interested students will be able to link to a brief confidential web-based screening survey. No in-person recruitment will occur at UH. Under supervision of the PI or research coordinator, Research Assistants will recruit participants using email addresses provided by the Registrar and posting of flyers.

7.2 Screening (pre-COVID). The screening survey was compiled of questions related to demographics (enrollment, age, class year, sex, gender identity), health behaviors (biggest issue affecting students’ overall health, stress, sleep habits), drinking behaviors (most alcohol consumed on an occasion in the past month, consequences related to drinking) and potential study conflicts (participation in another study, interview or focus group on the topic of alcohol use). Participants who were eligible were shown an eligibility message and re-routed to an online scheduling module to book an in-person baseline session.

7.3 Screening (post-COVID)

7.3.1 Screening for remote baseline sessions (Brown site)

To accommodate for online delivery, we changed eligibility criteria, to exclude students who were learning remotely away from the campus drinking environment. The following item was added in September 2020 to assess the individual’s living and learning situation: “How would you best describe your situation this semester?” (taking classes at Brown living at home, taking classes at Brown living in the Providence area, Note currently taking any Brown classes, Other:[fill in the blank]).

7.3.2 Screening for remote baseline sessions (Houston site)

No changes were made to the screening process at the University of Houston, as the majority of students commuted to campus prior to the pandemic.

7.4. Scheduling participants. Participants who meet screening criteria will be invited to schedule an individual in-person session using an online scheduling module (See Appendix A, Recruitment Materials, for details). The scheduling module will direct participants to select a date and time for their session and ask participants to provide their name, phone number and email address for further research study communications. A staff member will call, text, and/or email to confirm the appointment when it is made and will remind students of their appointment time and date one or two days before the scheduled appointment. At the in-person session, participants will provide written informed consent and complete the online baseline assessment

in a private room. Assignment to condition will take place after their baseline assessment; students will be stratified across conditions based on gender, a practice that has ensured baseline equivalence in drinking across conditions in several prior studies of college drinkers.

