8.2. Personalized Normative Feedback (PNF) Condition. Participants in the PNF condition will receive gender-identity specific personalized feedback regarding their alcohol use, consistent with previous NIAAA-funded trials using trained facilitator-delivered PNF as a brief intervention conducted by this team (e.g., R01AA014576). The PNF intervention contains both text and graphic information regarding 1) the student's own drinking quantity and frequency of drinking, 2) perceptions of typical drinking by same-sex students on campus (i.e., perceived descriptive norms), and 3) actual drinking rates by same-sex students' on campus (i.e., actual descriptive norms). Normative feedback for male or female identifying students will use data from same-sex students on campus, whereas normative feedback for non-binary or genderqueer students will use data averaged across all students on campus. The actual norms will be referenced to the survey from which norms were generated (date, N, and campus), which took place on both campuses in March 2019.

The RA will present the PNF sheets, populated by the participant's baseline data and will explain their format, where the normative data came from, and engage the participant in interpreting the graphic feedback. The RA will ask if the student has any questions about the information before concluding the session. This brief discussion is designed to be educational and clarifying, and to roughly equate the amount of interpersonal interaction to that in the CAA condition.

8.3. Assessment Only Control Condition. Participants in the assessment only control condition will receive no intervention. The only contact will consist of completing the baseline assessment in lab as well as email and telephone reminders to complete the 1-, 3-, and 6-month follow-up assessments.

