10. STATISTICAL CONSIDERATIONS

10.1. Sample Size. Power analyses focus on estimating a sample size large enough to detect “true” effects, thereby avoiding Type II errors. Sample size estimates were obtained for intervention contrasts. Necessary sample sizes were assessed via sample size and power equations for multi-level models using the Optimal Design software program. Based on previous findings using CAA and PNF approaches, we anticipate intervention effects relative to the neutral control condition to be in the small to medium range but at least comparable to effects which have been reported for personalized normative feedback, which are typically in the .28 range (e.g., Dotson et al., 2015). Based on the proposed sample size of 600, given four assessment points, we anticipate the ability to detect effects of intervention contrasts and moderation effects across the small to medium range. Considering maximum anticipated attrition rates of 15% (N=510) we will have .70, .80, and .90 power to detect effects sizes of $\delta = .24, .27, \text{ and } .32$, respectively.

10.2. Analysis Plan. Aims will be evaluated using generalized linear mixed models, an extension of general linear models allowing for multi-level data with non-normal distributions (e.g. Atkins, Baldwin, Zheng, Gallop, & [name], 2013; Hedeker & Gibbons, 2006). With respect to evaluating main effects of experimental conditions on drinking, each participant will provide up to four assessments (baseline, 1-month, 3-month, and 6-month follow-up data). Hypotheses will be tested using specific contrast vectors, using a general linear hypothesis framework (Fox, 2008).

Hypotheses associated with Aim 1 will be evaluated examining outcomes as a function of two dummy coded variables representing CAA and PNF with control as the reference group. Time X CAA outcomes will provide direct tests of differences in change between CAA and control groups. We will utilize a Bonferroni correction with Šídák adjustment for correlated outcomes to reduce alpha inflation associated with multiple outcomes (i.e., moderation attitudes, heavy drinking attitudes, dissonance, drinks per drinking day, binge frequency, peak BAC, alcohol consequences, and PBS use).

For these analyses, each participant will provide up to 4 repeated measures (i.e., baseline, 1-month, 3- months, 6-months), yielding up to 2400 Level 1 cases (repeated-measures) across 600 Level 2

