cases). Assuming outcomes follow a negative binomial distribution with a natural log link, the following model will be the basis for evaluating intervention effects as specified in Aim 1 hypotheses:

$$\text{Level 1: } \log(E[\text{DV}]_{ti}) = \pi_{0i} + \pi_{1i}(\text{Time})_{ti} + \varepsilon_{ti} \quad \varepsilon_{ti} \sim N(0, I\sigma^2_\varepsilon)$$

$$\begin{aligned} \text{Level 2: } \pi_{0i} &= \beta_{00} + \beta_{01}(\text{site})_i + \beta_{02}(\text{CAA})_i + \beta_{03}(\text{PNF})_i + \beta_{10} + r_{00i} \\ \pi_{1i} &= \beta_{10} + \beta_{11}(\text{site})_i + \beta_{12}(\text{CAA})_i + \beta_{13}(\text{PNF})_i + r_{10i} \end{aligned}$$

where t indexes repeated-measures and i indexes participants. Campus represents the differences between Brown and UH, CAA represents the difference between CAA and the Control group, and PNF represents the difference between PNF and the control group. DV_{ti} represents the outcome vector for each individual at each assessment point. Time_{ti} measures weeks since baseline. Hypotheses associated with Aim 2 will test the relative efficacy of CAA vs. PNF using a non-inferiority design. Following the procedures outlined by Schumi & Wittes (2011), we have consulted a recent metaanalysis to obtain an effect size estimate of PNF efficacy (vs. Control) on drinking quantity ($d = .289$, 95% CI [0.117, 0.451]) and consequences ($d = .157$, 95% CI[0.037, 0.278]) (Dotson, Dunn, & Bowers, 2015). Next, we use the lower bound of each confidence interval as the basis for deriving our margin with respect to declaring non-inferiority. Thus $M1 = 0.117$ for quantity and $M1 = .037$ for consequences; these represent the most conservative estimate of the PNF effect. Then we select a smaller margin (M2) that represents the largest acceptable loss of effect when CAA is compared to PNF. Using a conservative estimate of M2 (50% of M1; USFDA, 2016), we establish non-inferiority if we retain at least half of the effect of PNF. Thus, if the lower bound confidence interval for the effect of CAA vs PNF is larger than half the lower bound estimate of the effects on drinking quantity (.117/2 = .0585) and consequences (.037/2 = .0185), we will be able to declare CAA is non-inferior to PNF.

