Hypotheses associated with Aim 3 will evaluate mediators of intervention effects. We will follow procedures described by MacKinnon and colleagues (e.g., MacKinnon, Fairchild, & Fritz, 2007) to assess mediation. Mediation will test indirect effects using the AB products method with bootstrapped standard errors where A will represent effects of intervention contrasts by time interactions on mediators. B will represent the associations of mediators on subsequent drinking outcomes. Both A and B paths will control for baseline outcomes. Hypotheses associated with Aim 4 will follow a similar approach but will add prospective moderators and products of prospective moderators and contrasts

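### Assignment is stratified by gender but no analysis model has a gender term; the cost for the Time x CAA test is small (nil to about 2.4 points of power) and easily removed

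*Combined protocol and SAP*

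**What the plan says.** Section 7.4 describes assignment after the baseline assessment: "students will be stratified across conditions based on gender". It justifies this by the balance in baseline drinking that the practice gave in earlier studies. Gender is the only factor that section names. It does not say whether this means birth sex or gender identity, although both are collected (section 9.1.1).

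Section 10.2 prints the analysis model in full and says that "the following model will be the basis for evaluating intervention effects as specified in Aim 1 hypotheses". The Level 2 equations for the intercept and for the slope each contain site, CAA and PNF, and each has a random term. The definitions that follow match: "Campus represents the differences between Brown and UH, CAA represents the difference between CAA and the Control group", and PNF is defined in the same way. The test of interest is a contrast in change: "Time X CAA outcomes will provide direct tests of differences in change between CAA and control groups".

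The other models add no gender term. For mediation, "Both A and B paths will control for baseline outcomes". Aim 4 adds drinker identity, need for consistency and site. The analysis item in the Data Safety Monitoring Plan (Appendix E, item 13) repeats the power text and names no covariate.

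**The concern.** A factor that constrains randomisation is normally fitted in the analysis. Stratifying on it lowers the true variance of the treatment contrast. A model without it still counts the gender variance as noise, so its standard error is somewhat larger than the design warrants.

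The plan itself treats gender as linked to drinking. Section 7.4 stratifies on it for balance in drinking. The eligibility threshold differs by gender: "Past month heavy episodic drinking (for men, ≥ 5 drinks in one day, for women ≥ 4 drinks in one day". So does the feedback in section 8.2: "Normative feedback for male or female identifying students will use data from same-sex students on campus". What is at stake is a little precision and agreement between design and analysis. It is also better to settle gender adjustment in advance than to choose it after the results for eight Aim 1 outcomes are known.

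**Working it through.** **Inputs from the documents.** Three equal arms; N = 510 after 15% attrition, so 510/3 = 170 per arm; stated power .70, .80 and .90 at delta = .24, .27 and .32 (section 10.1); assessments at baseline and 1, 3 and 6 months. **Not in the documents:** alpha, sidedness and correlation for the power calculation, and any gender effect size. These are assumed below.

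**Step 1. The plan's own power.** With SD = 1, SE0 = sqrt(2/170) = .1085 and power = Phi(delta/SE0 - z).

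- Two-sided .05, no variance reduction: .600, .702, .839 (no match).
- One-sided .05: .715, .801, .904 (match).
- Two-sided .05 with SD = sqrt(1 - r²), r = .45: .698, .796, .910 (match).

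Two readings reproduce the stated figures, and the documents do not say which was used. The power text mentions no gender adjustment.

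**Step 2. A contrast of levels.** Let gender explain a share R of outcome variance and be balanced across arms. The true SE is SE0·sqrt(1 - R), while the model without gender reports SE0. At two-sided .05:

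- type I error without gender = 2[1 - Phi(1.96/sqrt(1 - R))]
- power without gender = Phi((delta - 1.96·SE0)/(SE0·sqrt(1 - R)))
- power with gender = Phi(delta/(SE0·sqrt(1 - R)) - 1.96)

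For R = .10 and delta = .27, the true SE is .1085 × .9487 = .1029. Power without gender is Phi((.27 - .2126)/.1029) = Phi(.558) = .712. Power with gender is Phi(2.624 - 1.96) = Phi(.664) = .747.

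| R (assumed) | Type I error without | Power without | Power with |
|---|---|---|---|
| 2% | .048 | .704 | .710 |
| 5% | .044 | .706 | .724 |
| 10% | .039 | .712 | .747 |

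The loss is 0.6 to 3.5 points. At one-sided .05 the pairs are .803/.808, .807/.818 and .813/.836, a loss of 0.5 to 2.3 points.

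**Step 3. The planned contrast, Time x CAA.** This was simulated on a linear log scale with 20,000 runs, 170 per arm, complete data, and visits at 0, 4.3, 13 and 26 weeks with time scaled to 26 weeks. Assumed values: half of each arm of each gender, random intercept SD .7, random slope SD .4, residual SD .5, gender effect on level 0.4, and a Time x CAA effect of 0.2 for power. The model with gender has it in both intercept and slope.

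| Gender-by-time (assumed) | Type I error without / with | Power without / with |
|---|---|---|
| 0 | .049 / .049 | .675 / .675 |
| 0.2 | .047 / .049 | .664 / .670 |
| 0.4 | .043 / .052 | .652 / .676 |

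With no gender-by-time effect the loss is nil, because the random intercept absorbs a pure difference in level. Otherwise it is 0.6 points (.670 - .664) or 2.4 points (.676 - .652). The Monte Carlo error of the type I figures is about sqrt(.05 × .95/20,000) = .0015, so .052 is compatible with .05.

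**Step 4. Why the two steps differ.** For Time x CAA, the relevant R is gender's share of the variance of individual slopes. The simulated SE of the contrast is .0831 with gender, and .0838 or .0859 without it. The shares are therefore 1 - (.0831/.0838)² = 1.7% and 1 - (.0831/.0859)² = 6.4%. The step 2 logic with these SEs and critical value 1.9665 gives power with gender of Phi(.2/.0831 - 1.9665) = .670. Without gender it gives Phi((.2 - 1.9665 × .0838)/.0831) = .664 and Phi((.2 - 1.9665 × .0859)/.0831) = .646. These losses, 0.6 and 2.4 points, agree with the simulation.

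**The case against.** The strongest reply is that the omission hardly touches the planned test. Aim 1 rests on within-person change, and the model has a random intercept, so a gender difference in how much students drink costs nothing. A loss needs gender to affect change, and the documents state no such effect. This stands, and it limits the size of the point.

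It can also be said that gender-specific thresholds may narrow gender differences on some outcomes, such as binge frequency and the attitude scales, so shares of 5% to 10% across all outcomes are speculative. That stands too: the shares are a range, not an estimate. A third reply is that section 10.2 calls its equations only the basis for evaluation, which leaves room for covariates. None is named, so the gap remains.

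A reader might infer that the stated .80 power at .27 would rise to .81, .82 or .84 for shares of 2%, 5% or 10%. Those values come from Phi(.27/(.0966·sqrt(1 - R)) - 1.96). The .0966 is not in the documents: it is back-solved from the stated power as .24/(1.96 + .524), on an unstated two-sided .05, and one-sided .05 with SE .1085 fits the stated power as well. For Time x CAA, R would also have to be a share of variance in change, so a link between gender and level of drinking does not support these gains.

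**Conclusion.** The mismatch is certain: gender is balanced at assignment and appears in no model. Its effect is minor. For Time x CAA the loss is nil to about 2.4 points of power. For contrasts of level it is about 0.6 to 3.5 points at two-sided .05. Both ranges rest on assumed gender effects, and the first also on a linear approximation to the negative binomial model with complete data.

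A reader might infer that leaving out a stratification factor makes the tests invalid. The calculations point the other way: without gender, type I error is .043 to .049 for Time x CAA and .039 to .048 for level contrasts. Nor is there bias, since gender is balanced across arms by design. That last statement assumes that dropout does not differ by gender in a way that also differs by arm, on which the documents are silent. This is a worthwhile refinement and no threat to the trial's conclusions.

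**What to change.** Add gender, coded as it was used at assignment, to both Level 2 equations: a term β04(gender) for the intercept and β14(gender), that is gender x Time, for the slope. The intercept term alone honours the stratification but gains nothing for Time x CAA; only the slope term can sharpen that test. Models built on the same equations for Aims 2 and 4 would carry the terms along, and the plan should say whether the mediation paths do.

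State whether birth sex or gender identity defined the strata, and how non-binary and genderqueer students, whom section 8.2 handles separately, were classed. Fix this before the analysis.

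The data are already collected. The cost is one extra parameter in each Level 2 equation with two gender levels, or two with three, plus a rule for a third level that may be too sparse to estimate in a negative binomial model with random intercept and slope.
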